4. STUDY DESIGN

4.1 Overall Design

This study is a single arm phase II prospective clinical trial in which patients with HCC who are deemed suitable for Y90 radioembolization will be recruited. Patients will undergo standard of care mapping study with ^{99}Tc -MAA to plan for Y90 radioembolization therapy. The additional, non-standard of care, intervention will be to do a second mapping study using low-dose Y90 (15 mCi) before the therapeutic Y90 radioembolization.

The distribution of MAA in terms of lung shunt fraction (LSF) and tumor to normal liver activity ration (TNR) will be compared to that of low-dose Y90. The treatment planning will be performed using standard of care MAA biodistribution using partition dosimetry model.

After administration of therapeutic Y90 dose, the actual dose delivered to tumor, non-tumoral liver (NTL) and lungs will be compared to the dose predicted by MAA and low-dose Y90.

The patients will be followed-up clinically and with imaging at 1, 3 and 6 months to determine tumor response, potential treatment related toxicity and to determine TDRT.

Hypothesis: Low dose Y90 microspheres as the treatment planning radiotracer will allow more accurate prediction of therapeutic Y90 liver biodistribution, which will enable us to perform prospective personalized dosimetry for every individual patient.

The results of this study will determine the safety and efficacy of using low dose Y90 as a direct surrogate for treatment planning to ensure delivering cytotoxic Y90 dose to the targeted tumor(s), while concomitantly minimizing liver and lung toxicity with more accurate prediction of therapeutic Y90 biodistribution. **Our long-term objective is to increase the likelihood of objective tumor response, prolonged progression-free survival (PFS) and overall survival (OS) in patients with HCC treated with Y90 RE.**

The study is a single-arm in study in which each patient will undergo two sets of mapping procedure before the actual Y90 therapy. One with standard of care ^{99}Tc -MAA and one with low-dose (15 mCi) Y90 microspheres. **Therefore, the additional intervention in the study is the second mapping procedure with low-dose Y90 microspheres.** Each patient will be used as their internal control to minimize selection biases. **Additional to standard of care Y90 SPECT/CT after therapy, the patient will undergo one PET/CT after low-dose Y90 and one PET/CT after Y90 therapy.**

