7.1.2 Dosing and Administration

Treatment will be administered on an *outpatient* basis. Reported adverse events and potential risks are described in Section 7. Appropriate dose modifications are described in Section 8. No investigational or commercial agents or therapies other than those described below may be administered with the intent to treat the patient's malignancy.

No dose escalation or dose expansion is planned in this procedure.

The treatment Y90 dose will be calculated using the partition model as detailed below:

The required therapeutic Y90 dose will be calculated using MAA SPECT, Y90 SPECT and Y90 PET. **Although all 3 sets of calculations will be made prospectively, the activity calculation based on MAA SPECT (the standard of care) will be used for actual treatment planning.** The activities calculated using Y90 SPECT and PET will be used for post-hoc analysis. Partition model to achieve cytotoxic Target Tumor Dose of >100 Gy will be utilized using the following formulas[7]:

- 1) **Desired Tumor Activity (GBq) = (100 Gy X Tumor Mass (Kg)) / 50**
- 2) **Targeted Normal Liver Activity (GBq) = Desired Tumor Activity (GBq) / TNR**
- 3) **Targeted Liver Lobe Activity (GBq) = (Targeted Normal Liver Activity + Desired Tumor Activity) (GBq)**
- 4) **Targeted Liver Lobe Dose (Gy) = Targeted Liver Dose Activity (GBq) X 50 / Liver mass (Kg)**

The liver and tumor mass will be determined using the volumes calculated by MIM software and assuming density of 1.03 g/cm³ [39]. It will be ensured that targeted liver dose remains below 50 Gy which has been shown to be safe with no sequela of radiation induced liver disease while ensuring the target tumor dose >100 Gy[7, 26].

5) Y90 Activity for administration (GBq) = Targeted Liver Lobe Activity (GBq) X (1+LSF)

Lung dose after therapeutic Y90 RE will be calculated using the following formula:

6) Lung Dose (Gy) = Y90 Activity to be Administered (GBq) X LSF X 50 / Mass of Lungs (Kg)

Lung Dose <30Gy will be ensured by reducing administered activity if needed (lung mass assumed at 1 Kg)[8].

The MAA, low-dose and therapeutic dose Y90 microspheres will be administered intra-arterially using the following technique:

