The patient will then be discharged from IR after removal of the radial sheath according to our standard protocol.

F. Low-dose Y90 PET/CT of chest and abdomen (Monday)

The patient will then undergo time of flight Y90 PET/CT with one or two bed positions depending on the patient's size. This will also occur on the same day and at the same location as the remainder of mapping day either at EUH or EUHM.

Schedule of Mapping Days:

7:30 AM-9:30 AM: 1st Angiographic study for mapping and MAA delivery

10:00 AM-11:00 AM: MAA SPECT/CT (Patient will go to nuclear medicine with radial/femoral arterial access sheath in place)

11:30 AM-1:00 PM: 2nd Angiographic study for low-dose Y90 delivery (After the procedure, patient's femoral sheath will be removed and hemostasis will be achieved with manual compression or closure device. If procedure performed via radial access, which is more commonly performed currently at Emory, the radial sheath will stay in and removed according to IR protocol after Y90 SPECT/CT.)

2:00 PM-3:00 PM: Y90 Bremsstrahlung SPECT/CT

3:00 PM-3:30 PM: Removal of the radial sheath at IR post procedural area and discharge.

4:30-5:30 PM: Y90 PET/CT.

Patient is free to go home after this.

G. Prospective Personalized Targeted Therapeutic Y90 Tumor(s) Dosimetry (Tuesday/Wednesday)

The required therapeutic Y90 dose will be calculated using MAA SPECT, Y90 SPECT and Y90 PET. **Although all 3 sets of calculations will be made prospectively, the activity calculation based on MAA SPECT (the standard of care) will be used for actual treatment planning.** The activities calculated using Y90 SPECT and PET will be used for post-hoc analysis. Partition model to achieve cytotoxic Target Tumor Dose of >100 Gy will be utilized using the following formulas[7]:

- i. **Desired Tumor Activity (GBq) = (100 Gy X Tumor Mass (Kg)) / 50**
- ii. **Targeted Normal Liver Activity (GBq) = Desired Tumor Activity (GBq) / TNR**
- iii. **Targeted Liver Lobe Activity (GBq) = (Targeted Normal Liver Activity + Desired Tumor Activity) (GBq)**
- iv. **Targeted Liver Lobe Dose (Gy) = Targeted Liver Dose Activity (GBq) X 50 / Liver mass (Kg)**

The liver and tumor mass will be determined using the volumes calculated by MIM software and assuming density of 1.03 g/cm³^[39]. It will be ensured that targeted liver dose remains below 50 Gy which has been shown to be safe with no sequela of radiation induced liver disease while ensuring the target tumor dose >100 Gy[7, 26].

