The duration of overall CR is measured from the time measurement criteria are first met for CR until the first date that progressive disease is objectively documented.

Duration of stable disease: Stable disease is measured from the start of the treatment until the criteria for progression are met, taking as reference the smallest measurements recorded since the treatment started, including the baseline measurements.

Progression-Free Survival

PFS is defined as the time from the date of first dose to the date of the first objectively documented progressive disease per m-RECIST or death, whichever is earlier. Patients who do not have the date of disease progression per m-RECIST or date of death will be censored on the date of the last evaluable tumor assessment. Patients who started a new antineoplastic regimen prior to disease progression per m-RECIST will be censored on the date of the last evaluable tumor assessment prior to receiving the new antineoplastic regimen. Patients whose disease progression or death appears after missing two consecutive tumor assessments will be censored on the date of the last evaluable tumor assessment. Patients who are lost to follow up will be censored on the date of their last evaluable tumor assessment. PFS will be estimated using the Kaplan-Meier method. The median and its 95% CI, along with the 25% and 75% quartiles will be summarized for all treated patients. OS will be defined as the date of first dose to the date of death. Patients who do not have a date of death will be censored on the last date for which the patient was known to be alive. OS will be analyzed similarly to PFS.

Response Review

All responses will be reviewed by an expert(s) independent of the study simultaneously as the results become available.

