10. STATISTICAL CONSIDERATIONS

10.1 Study Design/Endpoints

Primary Objective Endpoints:

A) Accuracy/Efficacy: The accuracy/efficacy of MAA as a predictor of therapeutic Y90 distribution will be compared to that of low-dose Y90.

H₀: Y90 will have the same LSF as MAA.

H_A: Y90 will have significantly less LSF than MAA.

H₀: Y90 will have the same TNR as MAA.

H_A: Y90 will have significantly higher TNR than MAA.

B) Safety: adverse events related to Y90 radioembolization and angiography will be document by physical examination, clinical laboratory test and cross-sectional imaging.

No statistical consideration applied to the safety portion of the primary end point as it is a single arm study in which every patients undergo both mapping procedures with MAA and low-dose Y90. Detailed safety analysis plan is outlined below in section 10.5.

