Time to event outcomes including TTP, PFS and OS will be evaluated using the methods of Kaplan and Meier, with a focus on graphical evaluation as well as early time-point and median estimates of survival distributions with 95% confidence intervals. The TTP, PFS and OS of each patient group at specific time points, such as 1 year, 3 years, and 5 years, etc. were also estimated alone with 95% CI. Cox proportional hazards models were further used in the multivariable analyses to assess adjusted effects of treatment (MAA vs Y90) on the patients' TTP, PFS and OS after

adjusting for other factors. The proportional hazards assumption was evaluated graphically and analytically with regression diagnostics. All data management and statistical analysis were conducted using SAS Version 9.4 (SAS Institute, Inc., Cary, North Carolina).

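### The Cox models for a treatment (MAA vs Y90) effect on TTP, PFS and OS have no contrast to estimate, because the study has one cohort and all of it is planned on MAA

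*Combined protocol and SAP*

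**What the plan says.** Section 10.5.4 (Analysis of secondary endpoints) defines TTP, PFS and OS from the start of protocol therapy and plans Kaplan-Meier estimation. It adds landmark estimates by group: "The TTP, PFS and OS of each patient group at specific time points, such as 1 year, 3 years, and 5 years". It then states the regression: "Cox proportional hazards models were further used in the multivariable analyses to assess adjusted effects of treatment (MAA vs Y90"), applied to all three outcomes after adjustment for other factors.

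The design is described elsewhere:

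- Section 10.1: "it is a single arm study in which every patients undergo both mapping procedures with MAA and low-dose Y90".
- Section 4.1, which also calls the trial single arm: "Each patient will be used as their internal control to minimize selection biases".
- Section 7.1.2, on how the therapeutic activity is set: "the activity calculation based on MAA SPECT (the standard of care) will be used for actual treatment planning". Section 8.1 repeats this and confirms that the activity administered is the one calculated from MAA SPECT.
- Section 8.1, on the low-dose Y90 calculations: "The activities calculated using Y90 SPECT and PET will be used for post-hoc analysis".

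Section 9.1.2 has its own time-to-event text. For PFS: "The median and its 95% CI, along with the 25% and 75% quartiles will be summarized for all treated patients". For survival: "OS will be analyzed similarly to PFS".

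**The concern.** A Cox model estimates a treatment effect by comparing, at each event, the patient who has the event with the others still at risk. It therefore needs patients who differ in treatment. Here MAA and low-dose Y90 are two scans of the same patient before one therapy, and only the MAA scan determines that therapy. The label MAA vs Y90 makes sense for a quantity measured once with each tracer in each patient, such as LSF or TNR. It does not make sense for a survival time, of which each patient has one.

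An analyst following section 10.5.4 would have to drop the model, or invent a grouping or data layout after the data are in. One obvious layout, copying each patient into both groups, runs without error and returns a hazard ratio of 1. That could be reported as evidence of no difference. Section 4.1 names longer PFS and OS as the long-term objective, so such a result could be over-read.

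**Working it through.** The documents give no hazard ratio, event count or power for this model, so there is no planned figure to reproduce. The question is whether the effect can be estimated at all.

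**Inputs**

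- Number of patients: 30 (section 10.2).
- Arms: one (sections 4.1 and 10.1).
- Tracer that sets therapy: MAA SPECT for every patient (sections 7.1.2 and 8.1).
- Outcomes per patient: one TTP, one PFS, one OS (section 10.5.4).
- Event times: none in the documents. The illustrative run assumes exponential times with mean 10 months, censoring at 24 months and one extra covariate, which gave 26 events in 30 patients. These assumptions do not affect the conclusion.

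**Layout 1: one row per patient**

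The Cox information on a log hazard ratio is the sum, over events, of the variance of the covariate in the risk set. For a binary covariate with share p at one level, each event contributes about p(1 − p).

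- Two equal groups: 0.5 × 0.5 = 0.25 per event.
- This design, all patients at one level: 1 × 0 = 0 per event.

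With events in all 30 patients the total is 30 × 0 = 0. In the illustrative run the partial log-likelihood was −71.826 at coefficients of −2, 0 and +2, and the second derivative for this term was 0. The likelihood is flat, so there is no estimate and no standard error.

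**Layout 2: two rows per patient, one labelled MAA and one Y90**

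Both groups now contain identical times and events, so the estimate must be HR = 1. Every risk set is split evenly, so each of the 2d duplicated events contributes 0.25, where d is the number of real events:

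- Information = 2d × 0.25 = d/2.
- SE = √(2/d) = √(2/26) = 0.277.

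The fitted values agree: HR 1.000 and SE 0.277 under both the Breslow and Efron treatments of ties. The apparent 95% interval is exp(±1.96 × 0.277), or 0.58 to 1.72. It looks like an ordinary imprecise null result, but it follows from copying the rows and would be centred on 1 whatever the data.

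**Other possible sources of a contrast**

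- Section 7.4.1 allows a second Y90 therapy in some patients. It does not create a group whose treatment was planned on low-dose Y90.
- Section 7.6 lets a patient stop low-dose mapping and stay on study. That would compare scout given with scout not given in an unplanned, non-randomized subset, and planning would still be by MAA.
- No section defines an external comparator.

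**The case against.** Several points on the other side are fair.

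- **Undefined under any coding.** A reader might infer that the hazard ratio and its standard error are always undefined. That is true only with one row per patient. With two rows the software returns numbers. The accurate claim is that no meaningful MAA-vs-Y90 hazard ratio exists.
- **Contradiction with section 9.1.2.** A reader might infer that section 9.1.2, which summarizes all treated patients, contradicts the reference in section 10.5.4 to each patient group. The documents do not support this. A whole-cohort summary and subgroup estimates can coexist, and section 10.5.4 does not say that its groups are MAA and Y90. The fault is an undefined term.
- **A survival comparison of planning methods.** A reader might infer that the trial sets out to compare survival under the two methods. Sections 7.1.2 and 8.1 are explicit that MAA sets treatment. The past tense of the Cox sentence, and the undefined cohorts in sections 10.5.3 and 10.5.4, look more like carried-over text than a deliberate aim.
- **The same label elsewhere.** A reader might extend the criticism to the linear models in sections 10.3 and 10.5.4 that use the same label. For LSF and TNR, MAA vs Y90 is a valid within-patient factor. For the dose-response quantities the text is ambiguous, and impossibility is not shown. Neither is part of this point.
- **Small consequence.** This stands. TTP, PFS and OS are absent from the objectives and endpoints in the synopsis and section 3, and the Kaplan-Meier estimates remain usable.

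None of this supplies a Y90-planned patient, so the objection narrows the point without removing it.

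**Conclusion.** The Cox contrast in section 10.5.4 cannot give a meaningful result and should be corrected before analysis. The information about an MAA-vs-Y90 hazard ratio is zero with one row per patient, and the ratio is 1.000 by construction with two. This rests only on the single-arm design, MAA-based planning for every patient, and one outcome per patient and endpoint. It does not depend on alpha, effect size or event count; the 0.277 is illustrative.

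The weight is modest. The affected analyses are secondary, have no power basis or decision rule, and are not listed in the synopsis or section 3. The primary paired comparison of LSF and TNR is untouched.

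**What to change.** In section 10.5.4:

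1. Delete the treatment (MAA vs Y90) term from the Cox models for TTP, PFS and OS.
2. Report single-cohort Kaplan-Meier estimates with 95% CI for all treated patients, in line with section 9.1.2.
3. Remove the reference to each patient group, or define it as named clinical subgroups. It should not mean MAA vs Y90.
4. If a Cox model is kept, label it exploratory and pre-name patient-level predictors that vary between patients, such as delivered tumor dose.

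The cost is a change of wording in the analysis plan. It needs no new data and no change to sample size or conduct.

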11. ADVERSE EVENTS: LIST AND REPORTING REQUIREMENTS

Adverse event (AE) monitoring and reporting is a routine part of every clinical trial. The following list of AEs and the characteristics of an observed AE will determine whether the event requires expedited reporting **in addition** to routine reporting.

11.1 Comprehensive Adverse Events and Potential Risks List

The Adverse Event and Potential Risks list provides a single list of reported and/or potential adverse events (AE) associated with an agent using a uniform presentation of events by body system.

Adverse Event List(s) for Y90 Radioembolization with Resin Microsphere [31]:

- Any procedure where the skin is penetrated carries a risk of infection. The chance of infection requiring antibiotic treatment appears to be less than one in 1,000.
- There is a very slight risk of an allergic reaction if contrast material is injected.
- Any procedure that places a catheter inside a blood vessel carries certain risks. These risks include damage to the blood vessel, bruising or bleeding at the puncture site, and infection. The doctor will take precautions to mitigate these risks.
- There is a risk that the microspheres may lodge in the wrong place, putting the patient at risk for an ulcer in the stomach or duodenum. This happens in approximately 2% of patients.
- There is a risk of infection after radioembolization, even if an antibiotic has been given.
- Because angiography is part of the procedure, there is a risk of an allergic reaction to the contrast material.
- **Non-Target Delivery of SIR-Spheres microspheres:** Inadvertent delivery of SIR-Spheres microspheres to extra-hepatic structures such as the esophagus, stomach, duodenum, gallbladder or pancreas may result in radiation injury to these structures. Meticulous angiographic technique must be employed to prevent the non-target delivery of SIR-Spheres microspheres to any extra-hepatic structures.
- **Radioembolization Induced Liver Disease (REILD):** Delivery of excessive radiation to the normal liver parenchyma may result in REILD – see description in Section 7. The risk of REILD may also be increased in patients with pre-existing liver disease. Consideration should be given to reducing the prescribed activity of SIR-Spheres microspheres in the following clinical settings1 : • Reduced liver functional reserve due to steatosis, steatohepatitis, hepatitis or cirrhosis • Elevated baseline bilirubin level • Small tumor

- burden (< 5% liver involvement) • Small liver volume (< 1.5 L) • Prior hepatic resection • Prior liver directed therapy • Extensive prior treatment with systemic chemotherapy and/or biologic therapies.
- **Radiation Pneumonitis:** High levels of implanted radiation and/or excessive shunting to the lung may lead to radiation pneumonitis. The lung radiation dose must be limited to \leq 30 Gy.

11.2 Definition of Adverse Events (AE)

Adverse event means any untoward medical occurrence associated with the use of an intervention in humans, whether or not considered intervention-related (21 CFR 312.32 (a)).

11.3 Definition of Serious Adverse Events (SAE)

An adverse event (AE) or suspected adverse reaction is considered "serious" if, in the view of either the investigator or sponsor, it results in any of the following outcomes:

- Death
- Life-threatening adverse event
- Inpatient hospitalization or prolongation of existing hospitalization
- A persistent or significant incapacity or substantial disruption of the ability to conduct normal life functions, or a congenital anomaly/birth defect.
- Important medical events that may not result in death, be life-threatening, or require hospitalization may be considered serious when, based upon appropriate medical judgment, they may jeopardize the participant and may require medical or surgical intervention to prevent one of the outcomes listed in this definition. (Examples of such medical events include allergic bronchospasm requiring intensive treatment in an emergency room or at home, blood dyscrasias or convulsions that do not result in inpatient hospitalization, or the development of drug dependency or drug abuse).

11.4 Classification of an Adverse Event

11.4.1 Severity of Event

For adverse events (AEs) not included in the protocol defined grading system, the following guidelines will be used to describe severity.

- **Mild** – Events require minimal or no treatment and do not interfere with the participant's daily activities.
- **Moderate** – Events result in a low level of inconvenience or concern with the therapeutic measures. Moderate events may cause some interference with functioning.
- **Severe** – Events interrupt a participant's usual daily activity and may require systemic drug therapy or other treatment. Severe events are usually potentially life-threatening or incapacitating. Of note, the term "severe" does not necessarily equate to "serious".

11.4.2 Relationship to Study Intervention

All adverse events (AEs) must have their relationship to study intervention assessed by the clinician who examines and evaluates the participant based on temporal relationship and his/her clinical judgment. The degree of certainty about causality will be graded using the categories below. In a clinical trial, the study product must always be suspect.

- **Definitely Related** – There is clear evidence to suggest a causal relationship, and other possible contributing factors can be ruled out. The clinical event, including an abnormal laboratory test result, occurs in a plausible time relationship to study intervention administration and cannot be explained by concurrent disease or other drugs or chemicals. The response to withdrawal of the study intervention (dechallenge) should be clinically plausible. The event must be pharmacologically or phenomenologically definitive, with use of a satisfactory rechallenge procedure if necessary.
- **Probably Related** – There is evidence to suggest a causal relationship, and the influence of other factors is unlikely. The clinical event, including an abnormal laboratory test result, occurs within a reasonable time after administration of the study intervention, is unlikely to be attributed to concurrent disease or other drugs or chemicals, and follows a clinically reasonable response on withdrawal (dechallenge). Rechallenge information is not required to fulfill this definition.
- **Potentially Related** – There is some evidence to suggest a causal relationship (e.g., the event occurred within a reasonable time after administration of the trial medication). However, other factors may have contributed to the event (e.g., the participant's clinical condition, other concomitant events). Although an AE may rate only as "possibly related" soon after discovery, it can be flagged as requiring more information and later be upgraded to "probably related" or "definitely related", as appropriate.
- **Unlikely to be related** – A clinical event, including an abnormal laboratory test result, whose temporal relationship to study intervention administration makes a causal relationship improbable (e.g., the event did not occur within a reasonable time after administration of the study intervention) and in which other drugs or chemicals or underlying disease provides plausible explanations (e.g., the participant's clinical condition, other concomitant treatments).
- **Not Related** – The AE is completely independent of study intervention administration, and/or evidence exists that the event is definitely related to another etiology. There must be an alternative, definitive etiology documented by the clinician.

